 - Time to LR, a secondary outcome, will be measured as the time from the date of randomization to the date of documented occurrence of the LR. Death before occurrence of LR will be treated as a competing risk. Study subjects who are alive and free of LR at their last evaluation will be rightcensored for Time to LR on the date of their last evaluation.
- Leptomeningeal disease (LMD), a component of CNS CE, will be diagnosed by imaging results consistent with this condition (either local or diffuse leptomeningeal disease) or by examination of spinal fluid positive for malignant cells.

- Time to LMD, a secondary outcome, will be measured as the time from the date of randomization to the date of documented first occurrence of the LMD. Death before occurrence of LMD will be treated as a competing risk. Study subjects who are alive and free of LMD at their last evaluation will be right-censored for Time to LMD on the date of their last evaluation.
- Radiation Necrosis (RN) of the treated lesions. If radiation necrosis is suspected based on imaging criteria (progression of contrast-enhancing mass that is associated with reduced perfusion on dynamic MRI, increased T2 flair/T2 hyperintensive signals within previous radiation treatment fields for the index lesion), then follow-up MRI imaging (with MRS, PET/SPECT as optional) will be obtained 4-6 weeks later to confirm the diagnosis of RN. The Time to RN will be back-dated to the initial imaging-findings date if the diagnosis of RN is confirmed by the follow-up imaging.
 - Stratified by surgical site versus non-surgical sites and the use of targeted therapy, cytotoxic chemotherapy, or immunotherapy
- Symptomatic Radiation Necrosis (SRN), a component of CNS CE, will be documented radiation necrosis of the treated lesions (see above) that is accompanied by symptoms (headaches, nausea, vomiting, or other neurologic symptoms).
 - Time to SRN, a secondary outcome, will be measured as the time from the date of randomization to the date of documented occurrence of the SRN. Death before occurrence of the SRN will be treated as a competing risk. Study subjects who are alive and free of SRN at their last evaluation will be right-censored for Time to SRN on the date of their last evaluation.

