Other Secondary Objectives include determining the other secondary outcomes described below, and comparing treatment arms for improvements with neoadjuvant SRS/SRT in (a) the rates of secondary yes/no outcomes such as Local Control, or (b) the 6-month, 12-month, 18-month, month rates of secondary time-to-event outcomes such as Duration of Local Control:

- Local Control.
 - Local Control will be defined as Complete Response [CR], Partial Response [PR], or Stable Disease [SD] of the index lesion resulting from the assigned treatment. It will be determined at the first evaluation following successful completion of either neoadjuvant or adjuvant SRS/SRT of all metastatic lesions and surgical resection of the index lesion.
 - Stratified by GTR or STR, piecemeal vs en bloc resection

- Treatment Failure will be defined either as Progressive Disease [PD] during the assigned treatment, or as the absence of Local Control at the first evaluation following successful completion of the assigned treatment.
- Duration of Local Control (DLC) will be measured as the time from the date when Local Control is first documented to the date when:
 - the treated lesions show documented evidence of LR or PD, or
 - the patient undergoes whole-brain radiotherapy, repeat SRS, repeat surgical intervention
- Time to distant in-brain failure.
 - Distant in-brain failure (DiBF) will be defined as the occurrence of any new parenchymal lesion outside of the planning target volume.
 - Time to DiBF will be measured as the time from the date of randomization to the date of occurrence of the DiBF. Death before occurrence of DiBF will be treated as a competing risk. Study subjects who are alive and free of DiBF at their last evaluation will be right-censored for Time to DiBF on the date of their last evaluation.
- Overall survival.
 - Overall survival (OS) will be measured as the time from the randomization date to the date of death for any reason. Study participants who are still alive at last follow-up will be right-censored for OS on the date of their last follow-up.
- Time to systemic therapy.
 - Time to initiation or re-initiation of systemic therapy will be measured as the time from the date when the assigned treatment (neoadjuvant versus adjuvant SRS/SRT) is successfully completed to the date when the systemic therapy is initiated or re-initiated.

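### Duration of Local Control is tested between arms only among patients who reached control, and it has no rule for death or censoring

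*Combined protocol and SAP*

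**What the plan says.** All of this is in the combined protocol and SAP.

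- **Other Secondary Objectives** makes both outcomes comparative. The aim is "comparing treatment arms for improvements with neoadjuvant SRS/SRT in (a) the rates of secondary yes/no outcomes such as Local Control", and in the 6-, 12- and 18-month "rates of secondary time-to-event outcomes such as Duration of Local Control".
- **Local Control** is complete response, partial response or stable disease of the index lesion. On timing: "It will be determined at the first evaluation following successful completion of either neoadjuvant or adjuvant SRS/SRT of all metastatic lesions", together with resection of the index lesion.
- **Treatment Failure** has two limbs: "Treatment Failure will be defined either as Progressive Disease [PD] during the assigned treatment, or as the absence of Local Control" at that same assessment.
- **DLC** is "measured as the time from the date when Local Control is first documented". It ends at local recurrence (LR) or progression of the treated lesions, or at whole-brain radiotherapy (WBRT), repeat SRS or repeat surgery. Nothing is said about death or censoring.
- **Time to LR**, by contrast: "Time to LR, a secondary outcome, will be measured as the time from the date of randomization". Death is a competing risk, and living patients without LR are censored at last evaluation. Time to LMD, SRN and DiBF follow the same pattern.
- **Statistical analysis plan** puts every time-to-event outcome under a 1-sided test at alpha 0.10. It names Fine and Gray for the primary outcome and a list of individual events, and the log-rank test for survival. DLC is in neither list. No analysis population is named, and the Local Control rate has no stated denominator or missing-data rule.

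**The concern.** Randomization makes the arms comparable at the date of randomization. DLC starts later, and only for patients whose treatment was completed and whose index lesion was controlled. Treatment can affect who those patients are. If one arm fails more often early, its worst-prognosis patients never enter the DLC comparison, and those who remain are a better-selected group. The 1-sided test could then favour the arm with poorer early control, or hide a real benefit of pre-operative treatment.

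The missing death rule adds to this. With deaths assumed at 32% per year, many controlled patients will die without a DLC event. Whether those deaths are censored, counted as the end of control or treated as competing events changes the 6-, 12- and 18-month rates, and the choice would be made after the data of an open-label trial are in hand.

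A smaller gap concerns the Local Control rate. A patient who stops treatment without progression, or who dies before the first assessment, meets neither the Local Control nor the Treatment Failure definition.

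**Working it through.** The plan gives no rate, sample size or power for Local Control or DLC, so there is no stated figure to reproduce. The main finding follows from the definitions; the arithmetic shows direction and scale.

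**1. Who enters each comparison**

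| Outcome | Clock starts | Patients included | Death rule | Censoring rule |
|---|---|---|---|---|
| Time to LR, LMD, SRN, DiBF | Randomization | All randomized | Competing risk | Last evaluation |
| DLC | Local Control first documented | Only those who reached control | None | None |

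A patient without Local Control has no starting date for DLC. No assumed figure is needed for this step.

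**2. Can the ranking reverse? (hypothetical; every input is assumed)**

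*Case A.* Half of patients have a failure hazard of 0.1 per year and half 0.6, the same in both arms once controlled. Control is reached in 95% of both halves pre-operatively, and in 95% and 75% post-operatively. Twelve-month failure is 1 − e^−0.1 = 0.0952 in the low-risk half and 1 − e^−0.6 = 0.4512 in the high-risk half.

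- Controlled patients only, pre-operative: (0.95×0.0952 + 0.95×0.4512)/1.90 = 27.3%.
- Controlled patients only, post-operative: (0.95×0.0952 + 0.75×0.4512)/1.70 = 25.2%.
- All randomized, no control counted as failure, pre-operative: 1 − 0.5×(0.95×0.9048 + 0.95×0.5488) = 31.0%.
- All randomized, post-operative: 1 − 0.5×(0.95×0.9048 + 0.75×0.5488) = 36.4%.

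*Case B.* 80% of patients are controlled on either arm (hazard 0.2), 10% only with pre-operative treatment (hazard 0.6), and 10% never. With e^−0.2 = 0.8187 and e^−0.6 = 0.5488, 12-month success is:

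- Controlled patients only: (0.8×0.8187 + 0.1×0.5488)/0.9 = 78.9% pre-operative versus 81.9% post-operative.
- All randomized: 0.8×0.8187 + 0.1×0.5488 = 71.0% versus 0.8×0.8187 = 65.5%.

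In both cases the arm with better early control looks worse on DLC and better in all randomized patients. Both cases ignore death and the interval from randomization to the first assessment.

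**3. How many patients could lack a Local Control status through early death?**

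Inputs: a competing death rate of 32% per year (Sample size section); maximum treatment windows of 15 + 15 = 30 days in Arm I and 15 + 30 = 45 days in Arm II (Design table); first scheduled MRI 2–3 months later (Follow-up), taken as 60–91 days. The formula is 1 − e^(−rate × days/365.25), with 32% read either as a hazard (0.32) or as an annual proportion (−ln 0.68 = 0.386).

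| | Days to first scheduled MRI | Deaths before it | Of 52 |
|---|---|---|---|
| Arm I | 90–121 | 7.6–12.0% | 3.9–6.2 |
| Arm II | 105–136 | 8.8–13.4% | 4.6–7.0 |

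These are upper-end figures. The windows are maxima, although any multi-day radiation course would lengthen Arm I, and expected survival under 3 months is an exclusion. The gap between arms is about 1.2–1.4 points (8.8 − 7.6 and 13.4 − 12.0), less than one patient of 52.

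**4. What an open denominator does to the Local Control rate (hypothetical)**

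Assume 90% control among assessed completers. If m of 52 patients do not complete and count as no control, the rate is 0.90×(52 − m)/52: 90.0%, 86.5%, 81.3%, 76.2% and 72.7% for m = 0, 2, 5, 8 and 10. On a completers-only denominator it stays at 90%. The plan does not say which applies.

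**The case against.** The strongest reply is that the sound comparison is already planned. Time to LR and the primary endpoint run from randomization with death as a competing risk. DLC is one of many secondary outcomes in a self-described pilot study, and no sample-size claim depends on it. This stands as a limit on the consequences. It does not repair DLC, which is planned as a comparison in its own right and also counts WBRT, repeat SRS and repeat surgery, which Time to LR does not.

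The illustrations are also open to attack. Case A needs a sixfold spread in hazard and a 20-point difference in control within the high-risk half, and still yields a reversal of only 2.1 points. With 52×0.95 = 49.4 and 52×0.85 = 44.2 controlled patients, the standard error of that difference is √(0.273×0.727/49.4 + 0.252×0.748/44.2), about 9 points, before any censoring. The Local Control rates beside it, 95% versus 85%, would also show which arm did better early. All of this stands: the cases show that the direction can mislead, not by how much it will.

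A reader might infer that the plan also drops non-completers from the Local Control rate. The documents do not support that. They call it a yes/no outcome, state no completers-only denominator, and count progression during treatment as Treatment Failure. Only patients who stop without progression or die before the first assessment are unclassified, and the plan is silent on how they count.

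Finally, counting every non-completer as no Local Control mixes tumour failure with unrelated reasons, such as a lesion that proves not to be a metastasis. That is a real cost, and reasons for non-completion should be reported alongside.

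**Conclusion.** The DLC point holds from the definitions alone. Followed as written, the plan tests between arms an outcome that exists only for patients who reached control, with no rule for death or censoring. That is not a comparison of the randomized groups. It should be corrected before analysis.

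The size of any bias cannot be derived from the documents. The reversals (27.3% versus 25.2% against 31.0% versus 36.4%, and 78.9% versus 81.9% against 71.0% versus 65.5%) rest wholly on assumed hazards and control rates. The only scale taken from the plan's own figures is early death: up to about 4–7 of 52 patients per arm might have no Local Control status, with a difference between arms of under one patient. That figure covers deaths only and uses maximum windows.

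For the Local Control rate the finding is a missing detail, not a planned exclusion. The primary endpoint, Time to LR and the other outcomes timed from randomization are unaffected, and nothing here suggests otherwise.

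**What to change.** 1. Make the between-arm durability comparison in all randomized patients, timed from randomization, using DLC's own events (LR or progression, WBRT, repeat SRS, repeat surgery). Count never reaching control as an event at time zero, treat death as a competing risk, and censor at last evaluation. State which rule takes precedence for a patient who dies before the first assessment. Name the test. Alternatively, rely on the planned Time to LR and note that it does not count WBRT, repeat SRS or repeat surgery.
2. Report DLC among controlled patients descriptively by arm, without a between-arm test, and give its death and censoring rules.
3. State the Local Control denominator as all randomized patients. Count those who stop without progression, or die before the first assessment, as no Local Control; give a rule for a missed assessment; tabulate the reasons.

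The cost is SAP wording; no new data are needed. The downsides are a less favourable Local Control rate (for example 81.3% instead of 90% if 5 of 52 do not complete) and a durability comparison that no longer describes controlled patients alone. The descriptive DLC summary still does that.

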- Time to subsequent brain treatment, including whole-brain radiotherapy (WBRT), will be measured as the time from the date when the assigned treatment is successfully completed to the date when the WBRT or other subsequent treatment is initiated.
- Radiation/Surgery toxicity
 - o The rate of symptomatic (≥grade 2) radiation/surgery toxicity

 Incidence of adverse events as graded by the National Cancer Institute (NCI) Common Terminology Criteria for Adverse Events (CTCAE) version 5.0

Study Design and Procedures

Design: This pilot study is a randomized, open-label, 2-arm active-controlled phase II clinical trial conducted at a single study site (UAMS) located in central Arkansas. Prospective enrollees will be screened based on the inclusion/exclusion criteria listed below in the *Study Population* section. Study-eligible candidates who agree to participate will be assigned by randomization to one of the 2 treatment arms shown in the table below:

Treatment Arm	Intervention/treatment
Experimental: Arm I (pre-operative SRS/SRT)	Radiation: Stereotactic Radiosurgery Undergo SRS/SRT Other Names:
Patients undergo SRS or SRT within 15 days of randomization followed by surgery within 15 days of radiation completion. Patients may undergo	Stereotactic External Beam Irradiation
	 stereotactic external-beam radiation therapy
additional SRS or SRT if disease returns after treatment.	stereotactic radiation therapy
	Stereotactic Radiotherapy
	 stereotaxic radiation therapy
	 stereotaxic radiosurgery
Active Comparator: Arm II (post- operative SRS/SRT) Patients undergo surgery within 15 days of randomization followed by standard-of-care SRS or SRT within 30	Undergo SRS/SRT Other Names: • Stereotactic External Beam Irradiation
	 stereotactic external-beam radiation therapy
days of surgery. Patients may undergo additional SRS or SRT if disease	stereotactic radiation therapy
returns after treatment.	Stereotactic Radiotherapy
	 stereotaxic radiation therapy
	stereotaxic radiosurgery

The dose, volume and fractionation of radiotherapy will be at the discretion of the radiation oncologist at the time of SRS/SRT depending on the size, location, and proximity to critical structures. Before treatment commences, each study participant will be stratified according to two stratification factors:

- Size of Index Lesion (<3 cm versus ≥3 cm)
- Number of Brain Metastases (4 or fewer versus 5 or more)

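### Duration of Local Control ends at any WBRT, repeat SRS or repeat surgery, so as written it can score patients whose treated lesions are controlled as having lost local control

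*Combined protocol and SAP*

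**What the plan says.** Under Other Secondary Objectives, Local Control is a response category of one lesion: CR, PR or "Stable Disease [SD] of the index lesion resulting from the assigned treatment". The clock for DLC then starts: "Duration of Local Control (DLC) will be measured as the time from the date when Local Control is first documented to the date when" one of two things happens. The first is that "the treated lesions show documented evidence of LR or PD, or" the second, that "the patient undergoes whole-brain radiotherapy, repeat SRS, repeat surgical intervention". The second end event gives no site, no reason for treatment and no instruction to censor.

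The same part of the protocol defines two neighbouring outcomes separately. Distant in-brain failure is "the occurrence of any new parenchymal lesion outside of the planning target volume". Later brain treatment has its own clock: "Time to subsequent brain treatment, including whole-brain radiotherapy (WBRT), will be measured as the time from the date when the assigned treatment is successfully completed". The arm table under Study Design and Procedures lets patients in both arms have "additional SRS or SRT if disease returns after treatment", again without limiting the site.

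DLC is the protocol's own example of a secondary time-to-event outcome whose 6-, 12- and 18-month rates are to be compared between arms. The Statistical analysis plan section lists LR, SRN, LMD, DiBF and WBRT as individual events to analyse. It does not name DLC.

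**The concern.** The first end event is a finding in a treated lesion. The second is something done to the patient. Documented failure of a treated lesion is already caught by the first, so the second mainly adds treatment given without such failure: SRS or surgery for a new distant metastasis, WBRT for distant or leptomeningeal disease, surgery for necrosis.

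A patient with every treated lesion controlled who has SRS for one new lesion would then have a distant in-brain failure, a subsequent brain treatment and a loss of local control. The first two are correct. The third is not what the outcome's name says.

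The population makes this a practical matter. Patients may enter with up to 10 lesions, and five or more is a randomization stratum. The trial is also open-label, so the second end event turns an unblinded treatment decision into an outcome event. At stake is whether a DLC difference, or its absence, can be read as a statement about local control.

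**Working it through.** The plan gives no rate, effect size or power for DLC, so there is no figure to reproduce. The check has two parts.

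**1. What the second end event adds**

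| Situation after Local Control is documented | First end event | Second end event | Already counted elsewhere |
|---|---|---|---|
| LR or PD of a treated lesion, then salvage | yes | yes, same or later date | Time to LR where it is LR; subsequent treatment |
| New distant lesion, SRS or surgery to it only | no | yes, read literally | DiBF; subsequent treatment |
| WBRT for distant disease or LMD, treated lesions controlled | no | yes on any reading | DiBF or LMD; subsequent treatment |
| Surgery for necrosis, no LR or PD | no | yes | SRN if symptomatic; subsequent treatment |

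The last three rows are patients without failure of a treated lesion.

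**2. Illustration of the effect on the comparison**

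Inputs:
- Local-failure hazard in the post-operative arm, L: 0.25 per year, borrowed from the planned CNS CE rate in the sample-size section (that rate also includes SRN and LMD), and 0.10 per year, assumed.
- Pre-operative arm: L/2, borrowing the plan's 50% reduction.
- Hazard of salvage without local failure, g: 0.1 to 0.6 per year, assumed, and assumed equal in both arms.
- Death hazard: 0.32 per year, from the sample-size section, treated here as a constant hazard.

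Formulas, with constant hazards:
- DLC hazard ratio = (L/2 + g) / (L + g)
- Non-local share of post-operative-arm DLC events = g / (L + g)

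| g per year | HR, L = 0.25 | Share, L = 0.25 | HR, L = 0.10 | Share, L = 0.10 |
|---|---|---|---|---|
| 0 | 0.50 | 0% | 0.50 | 0% |
| 0.1 | 0.225/0.35 = 0.64 | 29% | 0.15/0.20 = 0.75 | 50% |
| 0.2 | 0.325/0.45 = 0.72 | 44% | 0.25/0.30 = 0.83 | 67% |
| 0.4 | 0.525/0.65 = 0.81 | 62% | 0.45/0.50 = 0.90 | 80% |
| 0.6 | 0.725/0.85 = 0.85 | 71% | 0.65/0.70 = 0.93 | 86% |

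Twelve-month cumulative incidence of a DLC event is (h/(h + 0.32)) × (1 − exp(−(h + 0.32))), where h is the arm's total DLC hazard. For L = 0.25 it is 19.1% post-operative against 10.1% pre-operative at g = 0, and 41.6% against 35.4% at g = 0.4.

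*Higher local rate.* The background text cites local recurrence of about 44% for tumors over 3 cm, with no time frame. If that were a 12-month risk (an assumption), L = −ln(1 − 0.44) = 0.58 per year. The hazard ratio would then be (0.29 + 0.1)/(0.58 + 0.1) = 0.57 at g = 0.1 and (0.29 + 0.6)/(0.58 + 0.6) = 0.75 at g = 0.6.

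*Opposite direction.* Suppose there is no local effect (L = 0.25 in both arms) but retreatment for necrosis or LMD runs at 0.2 per year post-operatively and 0.1 pre-operatively (assumed). The DLC hazard ratio is (0.25 + 0.1)/(0.25 + 0.2) = 0.78, an apparent local benefit where none exists.

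**The case against.** The strongest reply is about wording. Under a local-control outcome, repeat SRS and repeat surgery may naturally mean retreating the same lesion, and the arm table uses a different word, additional, for later SRS/SRT. On that reading only WBRT remains a problem, and g shrinks to the WBRT-only rate. This stands as a possible intention. No section states it, though, so two abstractors could code one patient differently, and it cannot cover WBRT.

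There is also a rationale for stopping at WBRT. Local Control has to result from the assigned treatment, and WBRT irradiates the treated lesions too, so control afterwards cannot be credited to the assigned treatment alone. That is a reason to stop crediting follow-up time, but not to record a local failure.

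On size, a reader might infer that distant salvage is known to swamp DLC and must pull it toward no difference. The documents do not support that. They give no distant-failure or salvage rate, and their one local-recurrence figure points to a higher local rate in larger tumors. Equal salvage in both arms is also an assumption: the Potential benefits section raises immune activation, while calling it poorly studied in humans, and the protocol plans to compare distant failure between arms.

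Finally, overlap among secondary outcomes is not in itself an error, and Time to LR already provides a lesion-based measure without the retreatment end event. Both points stand and limit the importance of the problem.

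**Conclusion.** The concern holds as a defect in the definition of one secondary outcome. Read literally, the second end event records loss of local control in patients whose treated lesions are controlled. On the narrower reading it still does so for WBRT.

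The size is illustrative only. With a true local hazard ratio of 0.50, equal non-local salvage by arm and constant hazards, DLC would show about 0.64 to 0.93 over the main grid, with less dilution if local failure is more frequent. The direction is not fixed: the Potential benefits section expects less necrosis and LMD with pre-operative treatment, so retreatment for those could make that arm's local control look better than it is.

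A reader might go further and infer that the trial loses its measure of local effect. It does not. The primary outcome and Time to LR do not use the retreatment end event. The definition should still be changed, because DLC is a named between-arm comparison and the repair is short.

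**What to change.** Redefine the end of DLC as follows.
- DLC ends at documented LR or PD of a treated lesion, or at salvage SRS/SRT or surgery directed at failure of a treated lesion.
- SRS or surgery directed only at distant lesions does not end DLC. Follow-up of the treated lesions continues. It should not be a competing event either, because the treated lesions can still fail and those failures would be discarded.
- WBRT, or surgery for necrosis, given without LR or PD of a treated lesion is not scored as loss of local control. Because both affect the treated site, handle them by one prespecified rule (censoring or competing event), with the other as a sensitivity analysis.
- Record the target and reason of every salvage treatment.

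All such treatment stays counted in time to subsequent brain treatment. The same edit can close three related gaps: DLC has no stated rule for death or censoring, it starts on the index lesion but ends on the treated lesions, and the analysis section does not name it.

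The cost is a few sentences in the definition, one added data field (the documents do not say that target and reason are collected) and fewer DLC events.
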